5.5.11 Health-related quality of life (HRQoL)

Health-related quality of life (HRQoL) will be measured using the Medical Outcomes Study short form (SF-36) [21]. The SF-36 is a multi-purpose, short-form health survey with 36 questions. It yields an 8-scale profile of functional health and well-being scores as well as psychometrically-based physical and mental health summary measures and a preference-based health utility index. See the SIT-CR Baseline and Follow-up Questionnaires for the SF-36.

5.5.12 Maximal aerobic power (VO₂max)

Maximal aerobic power (VO₂max) will be estimated using a Modified Bruce Ramp Treadmill Test [22]. The Modified Bruce Ramp Treadmill Test is a sub-maximal multistage test for the prediction of aerobic capacity. Participants will be asked to walk on the treadmill with the incline and speed increasing every 3 minutes. During the test participants' heart rates (HRs) will be measured at the end of each 3 minute stage. The test is stopped once participants reach 85% of their estimated maximum HR (207-(0.7*age)). The test will be instructed by a research assistant and should take 10-15 minutes to complete. The HR values will be extrapolated to measure HRmax, and VO₂max estimated from the highest speed and grade that would have been achieved if the participant had worked to maximum (see SIT-CR Case Report Form).

5.5.13 Covariates

The following are possible confounders that will be used in the analysis.

Age: Each participant's age will be extracted from the CR patient file.

Sex: Participant's sex will be extracted from the CR patient file.

Education: Participant education is self-reported as part of the CR intake questionnaire and is defined as the highest education level attained from Grade 6 or less, up to 4+ years of college/university.

Marital status: Participant marital status is self-reported as part of the CR intake questionnaire, it is categorized as: "single", "married/common law", "divorced/separated", or "widowed".

Occupational status: Participants' current occupational status is self-reported as part of the CR intake questionnaire and is categorized as: "Full time, working for pay (35 hrs or more/wk)", "retired", "part time, working for pay", "unemployed (looking for work)", "not working, but have a job to return to (e.g. sick leave)", "unemployed", "not/never employed outside the home", or "presently on disability leave".

Occupation activity: Participants that are currently working, will be asked to rate their current occupation activity using the following categories: "mostly sedentary (e.g., desk-based job)",

"moderately active (e.g., mix of desk-based job and walking about)", "active and on your feet most of the time (e.g., teacher, nurse)", or "very active and physical (e.g., mail carrier, manual labour)"

Number of people in the household: Participants will be asked for the number of people in their household.

Season: The season/time of year the participant completed the majority of the intervention will be collected.

5.6 Statistical considerations

5.6.1 Sample size calculation

Pilot/feasibility studies are generally not designed with the power to detect intervention effects, which is the intention of future definitive trials. Pilot/feasibility studies are often carried out to be able to estimate an effect size for a larger trial. However, to provide guidance, we have estimated a sample size based on previous study effect sizes to detect differences in sedentary time. G*Power Version 3.1.9.2 power analysis and sample size software was used to calculate the sample size [23]. A minimal clinically important difference (MCID) for reductions in sedentary time (i.e. substituting sedentary time for light or moderate+ intensity PA) associated with improvements in cardiometabolic health, health-related quality of life and reduced mortality, has been estimated to be 30-60 minutes/day [24-26], with a cumulative effect (i.e. more is better). Unfortunately, as this study is a pilot-level RCT, there are not adequate resources to accommodate a large enough sample size to detect differences in 30 minute/day. Rather, there will be adequate power to detect a difference of 91 minutes/day, which was the average reduction in sedentary time from sedentary interventions found by the authors in a recent systematic review [6]. A total sample size of 32 participants, 16 per arm, is needed to detect a 91 minute/day difference in sedentary time at a 0.05 significance level with 80% power, an addition of 10% for those who do not complete the trial, and 5% for data missing at random, assuming a standard deviation of 94 minutes/day as found in a recent evaluation of sedentary time among CR graduates from the UOHI [5]. This sample size is sufficient to test the research hypothesis using t-tests to measure the difference in sedentary time between the intervention and control groups.

When the study is close to completion a sample size recalculation will be undertaken by the Research Methods Centre at the UOHI.

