4.3 Hypotheses

In adults with a diagnosis of coronary artery disease (CAD) (including heart attack, angina (chest pain), stent, percutaneous coronary intervention (PCI), and/or bypass surgery (CABG), providing sedentary prompts using a thigh-worn activity monitor (VTAP) will be superior to standard 8-week on-site CR programming in:

1. decreasing sedentary time;
2. increasing breaks from sedentary time;
3. increasing MVPA;
4. improving clinical outcomes (e.g. blood pressure, resting heart rate, blood lipids, HbA1c, body weight, BMI, waist circumference)
5. improving HRQoL, self-efficacy, symptoms of anxiety and depression;
6. improving measures of aortic stiffness; and
7. increasing maximal aerobic power (VO₂max).

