5.5 Measures

The primary objective of this study is to assess the feasibility and usability of the *activPAL3™* and the VTAP in a CR setting to inform the development of a larger RCT. This will be assessed by examining:

- Recruitment rates;
- acceptability of intervention and wearing the *activPAL3™* and the VTAP using an evaluation survey (see Evaluation Surveys);
- completion and drop-out rates; and
- intervention adherence using wear time logs.

The primary outcome of the intervention focuses on changes in sedentary time measured by self-report and the *activPAL3™* over the 8-week intervention period. These outcomes will provide standard deviations to estimate an effect size for a future RCT. Secondary outcome measures will include:

- changes in MVPA (self-reported and objectively measured);
- changes in clinical outcomes (e.g., body weight, BMI, waist circumference, blood pressure, total cholesterol, HDL, LDL, triglycerides, and fasting plasma glucose);
- changes in measures of anxiety and depression (HADS);
- changes in self-efficacy to reduce sedentary time and increase PA;

- changes in HRQoL (SF-36);
- changes in aortic stiffness (PWV); and
- changes in maximal aerobic power (Modified Bruce Ramp Treadmill Test).

Measures and study time-line are provided in **Table 1**.

5.5.1 *Sedentary time*

The primary objective of this study is to evaluate the feasibility and usability of the *activPAL3™* in collecting time spent sitting, standing and lying in an on-site CR program. From this, the primary outcome of the RCT will be changes in sedentary time as measured both by self-report (sitting time from the International Physical Activity Questionnaire [see SIT-CR Baseline and Follow-up Questionnaires], sitting time from a FITS log [see SIT-CR Baseline and Follow-up Questionnaires], a sitting time question from the CR intake questionnaire), and objectively measured by the *activPAL3™* over 7-days. See the provided PAL Technologies Ltd. End User Licence Agreement.

5.5.2 *Moderate-to-vigorous intensity physical activity (MVPA)*

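### The stated 80% power for 32 participants holds only for a one-sided test that the plan never declares; two-sided power is about 68% after the planned loss (75.5% with none)

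*Combined protocol and SAP*

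**What the plan says.** Section 5.6.1 first says that pilot studies are generally not powered for intervention effects and offers the calculation as guidance. It concedes that the study cannot detect 30 minutes/day. It then makes a definite claim: "there will be adequate power to detect a difference of 91 minutes/day". The total follows: "A total sample size of 32 participants, 16 per arm, is needed to detect a 91 minute/day difference in sedentary time". The stated α is 0.05 and the stated power 80%, and the total is said to include 10% extra for non-completion and 5% extra for missing data. The source of the SD is given as well: "assuming a standard deviation of 94 minutes/day as found in a recent evaluation of sedentary time among CR graduates". The section concludes: "This sample size is sufficient to test the research hypothesis using t-tests".

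Section 5.6.2 names independent t-tests, or the Wilcoxon-Mann-Whitney test for variables that are not normally distributed, as the primary analyses of sedentary time. It does not give the sidedness. Section 4.3 words the hypothesis directionally (prompting "will be superior to standard 8-week on-site CR programming in" decreasing sedentary time) but declares no one-sided test. Section 5.5 defines the outcome as a change: "The primary outcome of the intervention focuses on changes in sedentary time measured by self-report" and by the thigh-worn monitor.

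**The concern.** A significance level of 0.05 with no sidedness attached is normally read as two-sided. On that reading 32 is too few for the stated 80% power, even if nobody is lost.

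Three things depend on this:

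- **The power claim.** The plan says the sample is adequate and sufficient for a between-group test. A reader who takes 80% at face value would give a non-significant result more weight against a 91 minutes/day effect than the design supports.
- **The choice of test.** With sidedness open, it could be settled after the data are seen, when it might decide significance.
- **The recalculation.** Section 5.6.1 plans a sample size recalculation near completion. On the present inputs, the required evaluable number is 28 or 36 depending on a choice the plan does not make.

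A second, smaller question is whether an SD of sedentary time measured in programme graduates is the right SD for an outcome defined as change from baseline.

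**Working it through.** **Inputs (all from section 5.6.1).** Difference 91 minutes/day; SD 94 minutes/day; α = 0.05; target power 80%; allowances of 10% and 5%, about 15% in all; 16 per arm; two-sample t-test. The standardised difference is d = 91/94 = 0.968.

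**Method.** Power comes from the noncentral t distribution with n₁ + n₂ − 2 degrees of freedom and noncentrality d·√[n₁n₂/(n₁ + n₂)]. The critical value is the 95th percentile of t (one-sided) or the 97.5th (two-sided).

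**1. Reproducing 32.** One-sided, 14 per arm: noncentrality 0.968 × √7 = 2.56, critical value 1.706 on 26 df, power 80.2%. So 28 evaluable participants are needed.

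- Adding 15%: 28 × 1.15 = 32.2.
- Adding the two allowances in turn: 28 × 1.10 × 1.05 = 32.3.
- Dividing by the fraction retained: 28/0.85 = 32.9.

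The stated 32 matches the first two after rounding down.

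**2. The same inputs, two-sided.** At 18 per arm: noncentrality 0.968 × √9 = 2.90, critical value 2.032 on 34 df, power 80.5%. So 36 evaluable participants are needed. With the allowance this is 36 × 1.15 = 41.4 or 36/0.85 = 42.4, that is, 42 to 43. The normal approximation gives 17 per arm, or 34 before any allowance and 34 × 1.15 = 39.1 after it. Neither route gives 32.

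**3. Power of the design as planned.** A 15% loss leaves 32 × 0.85 = 27.2, taken as 14 and 13.

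| Evaluable | Two-sided 0.05 | One-sided 0.05 |
|---|---|---|
| 16 + 16 (no loss) | 75.5% | 84.9% |
| 14 + 14 | 69.4% | 80.2% |
| 14 + 13 (15% loss) | 67.6% | 78.8% |

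**4. Detectable difference.** Solving the two-sided formula for 80% power with SD 94 gives 96 minutes/day with 32 evaluable and 105.5 minutes/day with 27.

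**5. Level SD or change SD.** If the t-test is applied to change scores and the SD is 94 at both times, the change SD is 94·√[2(1 − r)], where r is the baseline/follow-up correlation. The documents give no r, so the values below are assumptions. Power is two-sided with 14 + 13.

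| Assumed r | SD of change | Power |
|---|---|---|
| 0.3 | 111 | 53% |
| 0.5 | 94 | 68% |
| 0.7 | 73 | 88% |

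Power reaches 80% at about r = 0.63.

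**The case against.** The strongest reply is that 32 does reproduce from the plan's own inputs, so the fault is an omission, not a miscalculation. A one-sided reading fits the directional hypothesis in section 4.3, and the documents do not state a two-sided test either. This stands as a description of how 32 was probably reached. It does not rescue the claim: a directional hypothesis does not declare a one-sided test, and the 80% is true only under that unstated choice.

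Second, this is a pilot. Feasibility and usability are the primary objective, section 5.6.1 disclaims power at the outset, and section 5.5 says the outcome data are to supply standard deviations for a later trial. This limits the consequences, and no passage plans to treat a null result as proof of no effect. But the same paragraph goes on to claim adequate power and a sufficient sample, for tests that section 5.6.2 calls primary.

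Third, the subsidiary points are weak. Adding instead of dividing for loss changes the total by less than one participant (32.2 against 32.9). The SD point shows uncertainty, not a shortfall: the range over r lies on both sides of 80%, and section 5.6.1 can be read as comparing sedentary time itself between groups. Both replies are fair. The main finding needs neither point.

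Finally, the planned recalculation does not correct the stated power, and it needs the sidedness settled first.

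**Conclusion.** The concern holds. With a difference of 91 and an SD of 94 minutes/day, 32 participants give 80% power only on a one-sided 0.05 test, which the plan does not declare. On a two-sided 0.05 t-test power is 75.5% without loss and about 68% after the planned 15% loss. The shortfall against the claim is roughly 12 percentage points, and the difference detectable with 80% power is about 105 minutes/day. If a one-sided test was intended, power with 27 evaluable is 78.8%, close to the claim.

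That the calculation was one-sided is inferred from the arithmetic; the documents do not say so. The 68% assumes that 94 is the SD of the variable analysed. For change scores the figure runs from 53% to 88% over assumed correlations of 0.3 to 0.7. The pilot purpose limits the harm, but the power statement is wrong as written for the test most readers would assume, and it should be corrected.

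**What to change.** Keep 32 participants and amend the text:

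1. State in sections 5.6.1 and 5.6.2 whether the primary test is one- or two-sided, before any comparison by arm is made.
2. Restate the power to match. If two-sided: 32 randomised and about 27 evaluable give 68% power for 91 minutes/day (SD 94, α = 0.05), and 80% power corresponds to about 105 minutes/day. If one-sided at 0.05: about 79% power with 27 evaluable.
3. Delete or qualify the sentence saying that the sample is sufficient to test the research hypothesis, and the statement in section 5.6.1 that power is adequate.
4. Say that 94 minutes/day is a between-person SD of sedentary time, say whether the t-test is on follow-up values or on change, and if on change give the power over a range of r as above.
5. Use the declared sidedness in the planned recalculation.

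The cost is protocol wording and a less favourable stated power. No participants, visits or measurements are added.

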5.6.2 Analysis strategies

Baseline clinical and socio-demographic characteristics will be compared between groups to identify any chance differences that may have occurred despite random assignment. Outcome variables will be screened to determine whether they meet assumptions of normally distributed random variables with equal variances, and a descriptive examination will be performed, including plotting of relationships by condition. Retention rate will be computed by condition.

For the primary analyses, group differences in objectively measured and self-reported sedentary time (using the average of seven days) over the two time points (baseline and 8 weeks) will be examined using independent t-tests for parametric variables and Wilcoxon Mann Whitney test for nonparametric

variables. Similar analysis techniques will be used for secondary outcomes of interest (i.e., *activPAL*-measured and self-reported weekly MVPA; BMI, waist circumference, total cholesterol, HDL, LDL, triglycerides, fasting blood glucose, blood pressure, resting heart rate, aortic stiffness, HRQoL scores, self-efficacy scores, HADS scores, and maximum aerobic capacity).

Table 1. Study measurement timeline.

Visit	Screen	Baseline week	Cardiac rehabilitation							
			Week 1	Week 2	Week 3	Week 4	Week 5	Week 6	Week 7	Week 8/ follow-up
Length of time needed	30 min	1-2 hours	45 min	30 min	30 min	30 min	30 min	30 min	30 min	1-2 hours
Informed consent	C, I									
Diagnosis	C, I									
Age	C, I									
Sex (male/female)	C, I									
Height		C, I								
Weight		C, I								C, I
Waist circumference		C, I								C, I
Blood pressure (Mobil-O-Graph)		C, I								C, I
Resting heart rate (Mobil-O-Graph)		C, I								C, I
Blood work (cholesterol, HDL, LDL, triglycerides, HbA1c)		C, I								C, I
MVPA (CR questionnaire + activPAL3)		C, I								C, I
Questionnaires (self-efficacy, HRQoL, anxiety/depression)		C, I								C, I
Aortic stiffness (Mobil-O-Graph)		C, I								C, I
Aerobic power (Bruce Treadmill Test)			C, I							C, I
Sedentary time (activPAL3™, IPAQ, CR Questionnaire)		C, I								C, I
7-day activity journal (FITS)		C, I								C, I
Wear-time log			I	I	I	I	I	I	I	
Sedentary feedback (VTAP)			I	I	I	I	I	I	I	
Feedback survey										C, I

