6.5 Withdrawal criteria

Participants have the right to withdraw from the study at any point in time. Personnel conducting the study have the right to withdraw participants from this study for any of the following reasons:

- The investigator feels it is in the participant's best interest.
- Participant needs medication/treatment that would interfere with the study.
- Participant does not follow the study staff's instructions.

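### The unadjusted two-sample tests of sedentary time are not protected under the plan's own missing-at-random allowance; adjusting for baseline and sex would close most of that gap at almost no cost

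*Combined protocol and SAP*

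**What the plan says.** - Section 5.6.1 adds "an addition of 10% for those who do not complete the trial, and 5% for data missing at random" to a sample size based on a difference of 91 min/day, "assuming a standard deviation of 94 minutes/day".
- Section 5.5 defines the intervention outcome: "The primary outcome of the intervention focuses on changes in sedentary time measured by self-report and the" activPAL3, over the 8-week intervention.
- Section 5.6.2 says that group differences over baseline and 8 weeks "will be examined using independent t-tests for parametric variables and Wilcoxon Mann Whitney test for nonparametric" variables. It does not settle whether the tested value is the change or the week-8 level.
- On loss, section 5.6.2 says only that retention will be computed by arm. No section gives an analysis population, an imputation or likelihood method, or a sensitivity analysis.
- Section 6.5 provides for loss after randomisation ("Participants have the right to withdraw from the study at any point in time") and lets staff withdraw participants who do not follow instructions.
- Section 5.5.13 lists covariates for use in the analysis. Baseline sedentary time is not among them, and section 5.6.2 contains no model that would use any of them.

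**The concern.** The sample-size section names a missing-data assumption, and the analysis section names tests which that assumption does not protect. An unadjusted test is computed on whoever has the value. That these participants alone enter the comparison is inferred from the tests and from the plan's silence; the plan does not say so in words.

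The protocol gives reasons why loss could differ by arm. Only Intervention participants wear the VTAP for weeks 1 to 7, are buzzed after 30 consecutive sedentary minutes, reapply the device each morning and return weekly logs (sections 5.4.2, 5.4.3 and 6.2). The burden may be greatest for those who sit most, and this arm has more instructions to breach under section 6.5. If so, the retained arms differ in baseline sedentary time, and an unadjusted comparison carries that imbalance into the estimate. Sections 5.5 and 5.6.1 intend the results to inform the effect size for a larger trial, so an avoidable bias could carry into its planning.

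**Working it through.** **The plan's own figure.** With difference 91, SD 94 (d = 91/94 = 0.968), alpha 0.05 and 80% power, a one-sided t-test needs 14 per arm, 28 in total, and 28 x 1.15 = 32.2. This reproduces 32. A two-sided test needs 18 per arm, and 36 x 1.15 = 41.4. Sidedness is not stated; that is a separate point. The allowance is 10% + 5% = 15%, and 0.15 x 32 = 4.8 participants, leaving about 27 (13.6 per arm).

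**Bias formula.** Inputs: SD 94 at both times (section 5.6.1 gives 94 without saying whether it is for a level or a change); baseline to week-8 correlation r, not in the documents, assumed 0.5 to 0.7; effect constant across baseline; loss depending on baseline only. Let s be the amount by which the mean baseline of retained participants falls below that of all randomised participants in an arm. Then:

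- bias of the change comparison = (1 - r) x (s_Int - s_Con)
- bias of the week-8 comparison = -r x (s_Int - s_Con)

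Positive bias hides benefit; negative bias creates it.

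**Same mechanism and amount of loss in both arms.** s_Int = s_Con, so both biases are zero. Simulation with 15% loss in each arm agrees, within simulation error.

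**Loss that differs by arm (assumed).** Control loss is at random, so s_Con = 0. Intervention loss is logistic in baseline. Integrating over a normal baseline gives s_Int:

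| Intervention loss | Log-odds per SD | s_Int | Change, r = 0.5 / 0.7 | Week 8, r = 0.5 / 0.7 |
|---|---|---|---|---|
| 20% | 1.0 | 16.3 | +8.1 / +4.9 | -8.1 / -11.4 |
| 25% | 1.5 | 26.0 | +13.0 / +7.8 | -13.0 / -18.2 |
| 5% | 1.0 | 4.4 | +2.2 / +1.3 | -2.2 / -3.1 |
| 5% | 1.5 | 6.1 | +3.0 / +1.8 | -3.0 / -4.3 |

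All biases are in min/day. A simulation of 6,000 trials per setting (16 per arm, no true effect, 20-25% loss in Intervention, 10% at random in Control) gave +4.8 to +13.3 for change and -8.3 to -18.4 for week 8. The Mann-Whitney test was not simulated.

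**Baseline-adjusted comparison.** Complete-case ANCOVA on the same simulated participants stayed within 0.8 min/day of the truth. It drops the same people, so the protection comes from conditioning on baseline.

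**Effect varying with baseline.** Take 15% loss in both arms with log-odds 1.1 per SD (s = 13.4) and an Intervention slope lower by 0.3. The bias is 0.3 x 13.4 = 4.0 min/day for both unadjusted tests, and main-effects ANCOVA shares it.

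**Standard errors at 13.6 per arm.**
- Week 8: 94 x sqrt(2/13.6) = 36.0.
- Change: 36.0 x sqrt(2(1 - r)) = 36.0 at r = 0.5 and 27.9 at r = 0.7.
- ANCOVA: 36.0 x sqrt(1 - r^2) = 31.2 and 25.7, before the small cost of estimating the slope. Simulation gives about 33 and 27.

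Two-sided power for 91 min/day at r = 0.5 is about 68% for either t-test and 80% for ANCOVA, again before that small cost.

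**The case against.** Much of the case on the other side stands.

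- A reader might infer that these tests are generally biased under missing at random, or are unbiased only if loss is unrelated to sedentary time within each arm. That is too strong. Strong baseline-related loss shared by both arms leaves the arm difference unbiased when the effect is constant.
- A reader might blame the dropping of participants with one recording. ANCOVA drops them too and is not biased in these settings. With two time points, baseline-only recordings add little to the arm contrast, and they remain usable for describing sedentary time.
- A reader might take the 15% as a forecast that this share will have no usable outcome. It is a sample-size allowance. Only "5% for data missing at random" carries that label; no mechanism is given for the 10% who do not complete.
- The documents give no differential loss, no link to baseline and no r. A 25%/10% split averages 17.5%, above the plan's 15%.
- The biases are smaller than one trial's standard error. The largest applies only to a week-8 test, whereas section 5.5 speaks of change.
- The primary objective is feasibility, section 5.6.1 concedes that 30 min/day is out of reach, and computing retention by arm would reveal unequal amounts of loss.

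These points limit the size of the problem but do not remove the mismatch between assumption and test. Retention rates do not show who was lost, and a confidence interval reflects sampling error but not this bias.

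**Conclusion.** The point holds in a conditional form. The plan assumes that some data are missing at random but uses unadjusted comparisons that this assumption alone does not protect. Bias arises only if baseline-related loss differs by arm or the effect varies with baseline; otherwise it is about zero. Under the assumed differential loss it is about +5 to +13 min/day for change and -8 to -18 for week 8. At 5% loss per arm it is about 2 to 3 (1.3 to 4.3 in absolute size over the range shown). For comparison, the protocol's minimal important difference is 30 to 60 min/day and the standard error is roughly 26 to 37. These figures rest on SD 94, r of 0.5 to 0.7 and a loss pattern that the documents do not supply. The sign depends on which value is tested, and section 5.6.2 leaves that open. The effect on this pilot is modest; the change is worth making because it costs almost nothing and also improves precision.

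**What to change.** In section 5.6.2, make the primary analysis of activPAL3 sedentary time a comparison of week-8 values by assigned arm, adjusted for baseline sedentary time and sex (the stratification factor), and report the arm difference with a 95% CI. ANCOVA is enough. An equivalent constrained longitudinal model, with small-sample degrees of freedom, would also keep participants who have either recording.

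This removes bias from baseline-driven loss when the effect is constant across baseline, and it is more precise than the change-score or the week-8 t-test. It does not cure loss that depends on the unseen week-8 value, or an effect that varies with baseline. A sensitivity analysis that shifts the missing values of non-completers is optional.

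Cost: a few sentences in section 5.6.2 and a standard model, with no new data and no change to the planned 32 for this point. The downside is that a model-based estimate replaces a simple t-test.
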